### **AMENDMENT #8**

The study referenced above has been amended as outlined below:

1. [name] "Cohort Study of CAG Repeat Length and Prostate Cancer" has been added as Appendix 19.8. Associated changes in the protocol body include the addition of [name] address on page 2, the addition of Objective 1.9, the addition of background information on the cohort study of CAG repeat length on page 18 and the addition of a sentence in Section 11.14 covering Objective 1.9.
2. The phrase "biopsy proven" has been changed to "histologically proven" throughout the protocol to recognize that prostate cancer may be detected via TURP as an alternative to biopsy. The change is reflected in Sections 1.1, 10.0 (1st paragraph), 19.4 (1st paragraph) and Appendix 19.7 (Sections 3.1, 3.7 and 3.9). Additionally, several references to "biopsies" were changed throughout Section 11.0 to better reflect protocol intent.
3. Additionally, [name]. has replaced [name]., Ph.D. as the Merck, Sharpe and Dohme contact person for this study. This change is reflected on page 2.
4. In Section 8.2 in the first sentence, the words "clinically acceptable" were added to describe symptoms for which patients should be requested to remain on study drug.
5. Finally, this study will not use the new NCI Common Toxicity Criteria version 2.X. This clarification is noted in Section 8.2 and 16.0 (ADR/AE Guidelines).

Replacement pages are enclosed for pages 2, 4, 18, 26, 28, 29, 31 - 33, 36, 58, 71 and 74 - 76. Pages 81 - 90 have been added as the new Appendix 19.8. Please insert them into your copy of the protocol.

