- 11.5 **SENSITIVITY/SPECIFICITY OF DRE, TRUS, AND BIOPSY:** It is known that finasteride generally reduces the prostate gland size, and therefore has the potential to affect the sensitivity and specificity of DRE and TRUS; furthermore, finasteride could affect the sensitivity of the prostate biopsy. The directions and degrees of finasteride's effect on these sensitivities and specificities are unknown at this time, and will be investigated as part of this study. These possible sensitivity and specificity effects, if they exist, would seriously compromise the validity of this trial since the design of this trial had to be based on the following assumption:

**CRITICAL ASSUMPTION:** Finasteride does not affect the sensitivity or specificity of the DRE or the TRUS, nor does finasteride affect the sensitivity of the prostate biopsy.

- 11.6 **BPH AND TURP:** It is theoretically possible that the incidence of benign prostatic hypertrophy (BPH) prior to the seven year biopsy in the finasteride arm will be less than in the placebo arm due to the potential of finasteride to prevent BPH. If there are relatively more BPH incident cases in the placebo arm then it is possible that there will be relatively more transurethral resections of the prostate (TURP) in the placebo arm, from which it follows that there could be relatively more incidental prostate cancers found in the placebo arm through the use of TURP. The implementation of a procedure for balancing the numbers of TURPs between the arms is not planned because it would interfere too much with standard urological practice. Thus, there is potential for a bias of unknown magnitude in favor of the finasteride arm with respect to prostate cancer incidence prior to the seven year biopsy. This potential bias will not be corrected by the seven year biopsy unless the sensitivity of the seven year biopsy is equal to or exceeds the sensitivity of the interim TURPs, but the relationship of these sensitivities is not known at this time. If this TURP bias exists then this trial will be anticonservative. It follows that the following assumption is necessary:

**CRITICAL ASSUMPTION:** It is assumed that any bias resulting from TURPs in BPH incident cases will be negligible.

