- 11.9 **PRIMARY ANALYSIS:** The primary outcome analysis will consist of testing the coefficient of the arm indicator variable in a logistic regression model for the probability of prostate cancer. The logistic regression model will include covariates for all stratification factors except the Study Center. This analysis will include all subjects who have a biopsy at seven years plus the subjects who were found to have prostate cancer (histologically-proven) prior to seven years. The power computations which follow use standard formulas for computing the power when comparing proportions. The actual power of the trial is computed based on  $p_{0r}$  and  $p_{1r}$ , the probabilities adjusted for assumed degrees of contamination and nonadherence.

- 11.10 **POWER:** Based on 9,000 participants per arm, the graphs in Figure 4 illustrate actual power for an assumption of 60% of participants biopsied, true probability of prostate cancer in the placebo arm ( $p_0$ ) of 4% and 6%, unadjusted percent differences of 25% and 30%, and ranges for degrees of placebo arm contamination and finasteride arm nonadherence as described previously. If the desired actual power is 90% or above then the graphs in Figure 4 illustrate that this power is achievable provided: the unadjusted percent difference is 30%, the true probability of a positive biopsy in the placebo group ( $p_0$ ) is close to 6%, and the degree of placebo arm contamination and finasteride arm nonadherence do not become excessive. There is much less latitude for an unadjusted percent difference of 25%.

In particular, using the 60% biopsy rate, the power is 92.1% for an adjusted difference of 24.7% from a 6% placebo arm prostate cancer rate using a 5% placebo group contamination and a 14% finasteride arm nonadherence. This power computation is labeled in the fourth graph in Figure 4. These conditions are believed to be achievable if the trial is tightly controlled.

11.11 POWER FOR SIDE-EFFECTS AND ADVERSE EVENTS: The reported experience for one year of treatment with placebo (n=300) versus finasteride 5 mg (n=300) by the manufacturer includes the following:

	Finasteride	Placebo
decreased libido	4.7%	1.3%
ejaculatory disorder	4.4%	1.7%
impotence	3.4%	1.7%

The power using the first 1800 subjects per arm to detect differences in these measures (including a combined measure of sexual dysfunction) is shown below. The 1% one sided alpha level is used to permit five multiple comparisons at the 5% level.

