### **TURP Specimens:**

It is anticipated that some participants may undergo transurethral resection of their prostates for benign obstructive disease during the course of the study. Some of these patients may be found to have Stage A carcinoma in their resection specimens. In any case, all of the tissue resected should be submitted for histologic processing at the originating institution. If the institution is unwilling to process the entire specimen, the wet, fixed TURP fragments can also be submitted to the Pathology Core Laboratory.

The fresh prostate chips will be fixed in 10% neutral buffered formalin for a minimum of 24 hours and a maximum of 72 hours. Following fixation, the chips will be processed for routine paraffin embedding. All of the paraffin infiltrated chips will be embedded, using as many cassettes as required to sample every chip. Following embedding, each paraffin block will be faced until all the chips are exposed. Two histologic slides will be made from each block for diagnostic purposes, then the block faces will be sealed with molten paraffin. After diagnosis has been made, one set of the histologic slides and all the paraffin blocks will be sent to the Pathology Core Laboratory for archival storage.

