### 3.7 Endpoint

The endpoint for this study will be histologically -proven presence or absence of prostate cancer, assessed for most participants at the termination of the trial. The majority of prostate cancer cases detected will be asymptomatic.

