### 3.8 Final sample and sample size

The control group is the primary group of interest for the proposed study of diet and prostate cancer. The intervention group is of less interest for several reasons: 1) finasteride may affect diet or weight, e.g., some hormone treatments lead to weight changes; and 2) if lower dietary fat intake and finasteride both reduce the risk of prostate cancer through hormonal mechanisms, there may be an interaction between the effect of diet and finasteride on prostate cancer. Although our primary analysis will be among control men, we will collect all measures on intervention and control groups given the blinded nature of the PCPT design. We do plan to analyze separately the results in the intervention group.

Only men with a positive biopsy before the end of the trial or a biopsy (positive or negative) at seven years will be considered to have endpoint information. The PCPT estimates that 5,400 (60%) of the 9,000 control men will have complete exposure and endpoint information. This is based on the following: 20% mortality (seven-year mortality of U.S. men age 55 - 70, median age 63); 15% loss to follow-up (our experience in the CARET trial); and 5% biopsy refusal at seven years.

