#### 2.0 BACKGROUND

In January 2001, the first of the men who were randomized on PCPT will undergo their end of study biopsies. During the period between early 2001 and mid-2004 (seven years after the last man was randomized) all men who have not previously been diagnosed with prostate cancer will have end of study biopsies scheduled. Under the current study design, the end of study biopsy is the termination point for follow-up. Participants who refuse the end of study biopsy are to have their follow-up terminated at the date of their final annual visit, seven years after their entry to the trial.

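### Appendix 19.7 Section 3.8 ties diet-study endpoint status to biopsy, so read literally it leaves out cancers proven only at TURP, which Sections 3.7 and 11.9 count as cases

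*Supplement*

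**What the plan says.** - **Analysis set, diet study (Appendix 19.7, Section 3.8).** The rule on whose endpoint status counts as known reads: "Only men with a positive biopsy before the end of the trial or a biopsy (positive or negative) at seven years will be considered". Further on, the section gives 5,400 of 9,000 control men (60%) with complete data.
- **Endpoint, diet study (Appendix 19.7, Section 3.7).** "The endpoint for this study will be histologically -proven presence or absence of prostate cancer". Sections 3.1 and 3.9 use the same term for the outcome being modelled.
- **Analysis set, main trial (Section 11.9).** Men with a seven-year biopsy, "plus the subjects who were found to have prostate cancer (histologically-proven) prior to seven years".
- **What the term is meant to cover (Amendment #8, item 2).** Histologically proven was adopted "to recognize that prostate cancer may be detected via TURP as an alternative to biopsy". The diet-study sections listed for the wording are "Appendix 19.7 (Sections 3.1, 3.7 and 3.9"). Section 3.8 is not among them.
- **Who gets the seven-year biopsy.** Section 7.8 limits it to men still on protocol treatment, and Section 7.14e item 1 ends protocol treatment when prostate cancer is diagnosed. Appendix 19.10, Section 2.0, agrees: "all men who have not previously been diagnosed with prostate cancer will have end of study biopsies scheduled".
- **Whether TURP cancers are expected.** Appendix 19.4, on TURP specimens: "Some of these patients may be found to have Stage A carcinoma in their resection specimens". Section 11.6 adds that "there could be relatively more incidental prostate cancers found in the placebo arm through the use of TURP".

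**The concern.** The appendix defines its endpoint one way and its analysis set another, and the two disagree about one identifiable group of men. Everyone in that group is a case, so the exclusion depends on the outcome and on how it was found.

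Three consequences follow if Section 3.8 is applied as written:

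- The diet analysis and the main trial would use different case definitions for the same placebo men.
- Secondary Aim d compares the finasteride effect across quartiles of fat intake using both arms. If TURP cancers are commoner on placebo, as Section 11.6 allows, cases would be removed unequally by arm.
- TURP follows BPH, and Appendix 19.7 Section 2.2 proposes hormonal routes for fat and fiber. Independence of the exclusion from the exposures therefore cannot simply be assumed. The documents give neither a direction nor a size for any such link.

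Two analysts working from this appendix could build different datasets.

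**Working it through.** **Does biopsy in Section 3.8 already include TURP?** Sections 7.11 and 12.1a list prostate biopsy and TURP as separate procedures, and Amendment #8 calls TURP an alternative to biopsy. On the protocol's own usage, a TURP finding is not a positive biopsy.

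**A man with cancer found only at TURP in year 4, taken through each rule:**

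| Rule | Result |
|---|---|
| 19.7 Section 3.7: histologically proven cancer | Case |
| Main protocol 11.9: histologically proven before seven years | Case, included |
| 19.7 Section 3.8, first branch: positive biopsy before trial end | Not met, unless a later biopsy is also positive |
| 19.7 Section 3.8, second branch: biopsy at seven years | Not met: off treatment (7.14e item 1, 7.8) and already diagnosed (19.10 Section 2.0) |

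He fails both branches of Section 3.8 and is a case everywhere else.

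**The appendix's own figures, reproduced.** The inputs are in Sections 3.8 and 3.9: losses of 20%, 15% and 5%; p = 0.06; two-sided 5% significance; 80% power.

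- Men with data: 9,000 × (1 − 0.20 − 0.15 − 0.05) = 5,400. Per quartile: 5,400 / 4 = 1,350.
- d = (1.960 + 0.842) × √(2 × 0.06 × 0.94 / 1,350) = 0.0256 (stated .026).
- From the stated .047 and .073: odds ratio = (0.073/0.927) / (0.047/0.953) = 1.597 (stated 1.60). Without rounding it is 1.585.
- Expected cases: 0.06 × 5,400 = 324.

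These figures hold. The point concerns who is counted, not this arithmetic.

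**How much could it matter?** No TURP cancer count is given, so let f, the TURP-only share of all cases, be an assumption running from 2% to 20%. The answer turns on what the 6% means.

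- *Reading A: the 6% includes TURP cancers, and Section 3.8 removes them.* Cases = 324(1 − f) and men = 5,400 − 324f. For f = 5%, 16.2 cases go, leaving 307.8 of 5,383.8 men. Then p = 0.0572, n = 1,346 per quartile, d = 0.0251 and the odds ratio is 1.60.
- *Reading B: the 6% covers men who have biopsies, as Section 3.9 words it.* Section 3.8 then takes nothing from the 324, and the reworded rule adds 324f/(1 − f) cases. For f = 5%, 17.1 are added, giving 341.1 of 5,417.1 men. Then p = 0.0630 and the odds ratio is 1.57.

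| Assumed f | A: cases lost | A: detectable OR under 3.8 | B: cases gained | B: detectable OR after rewording |
|---|---|---|---|---|
| 0% | 0 | 1.585 | 0 | 1.585 |
| 2% | 6 | 1.59 | 7 | 1.58 |
| 5% | 16 | 1.60 | 17 | 1.57 |
| 10% | 32 | 1.62 | 36 | 1.55 |
| 20% | 65 | 1.67 | 81 | 1.51 |

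On either reading the effect on precision is slight unless TURP-only cancers form a sizeable share of all cases.

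**The case against.** The best reply is that Section 3.8 uses positive biopsy as shorthand for a detected cancer. The main protocol does so too. Section 11.4 describes the same 40% loss in terms of men with no positive biopsy, although Section 11.9 analyses all histologically proven cancers. Section 11.10 calls the placebo probability that of a positive biopsy, where Section 11.8 defines it as detectable cancer. Section 3.8 mirrors Section 11.4, down to the 20/15/5% losses. This stands as an explanation of how the wording arose. It does not remove the conflict, because Section 3.8 is the explicit inclusion rule and says that only these men qualify.

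Numbers are also likely to be small. Eligibility excludes men with an abnormal DRE, urinary retention, a wish for immediate treatment of obstruction, an AUA score of 20 or more, or a PSA above 3 ng/ml. That stands.

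Counting TURP cancers is not bias-free either. Section 11.6 names TURP detection as a possible bias, and a TURP-negative man who misses the seven-year biopsy stays out under any of these rules. That stands, and it is why a sensitivity analysis is needed.

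Two stronger readings are tempting:

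- A reader might infer that the stated 80% power is overstated. Section 3.9 words the 6% for control men who have biopsies, so the stated power need not depend on TURP cancers at all.
- A reader might see a second conflict between the end of the trial in Section 3.8 and seven years in Section 11.9. Section 7.14e item 3 treats seven years from randomization as termination of the study, so there is none.

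**Conclusion.** The current text contradicts itself on who counts as a case in the diet study. Read literally, Section 3.8 leaves out men whose cancer is proven only at TURP, while Sections 3.1, 3.7, 3.9 and 11.9 count them. This rests on the plain sense of only in Section 3.8, on Amendment #8 for the meaning of histologically proven (Section 3.7 does not itself name TURP), and on the man having no positive biopsy as well.

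A reader might conclude that these cases will certainly be dropped. The documents do not establish that: an analyst may follow Section 3.7, and a missed conforming edit is the likeliest cause. The number is not given and is probably small, and no loss of the stated power is shown. What remains is an outcome-dependent exclusion at odds with the main trial's definition, with possible imbalance by arm in the finasteride-by-fat analysis. The main trial's primary analysis is not affected. The wording should be corrected, but the study does not fail because of it.

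**What to change.** Reword the Section 3.8 rule so that endpoint information exists for men with histologically proven prostate cancer from any prostate tissue (biopsy, TURP or other) before the end of the trial, and for men with a seven-year biopsy whatever its result. This matches Sections 3.7 and 11.9.

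Add a sensitivity analysis that leaves out TURP-only cancers, for both the fat analysis in control men and the finasteride-by-fat analysis, and report the number of such cancers by arm. This shows any effect of the TURP detection route that Section 11.6 raises.

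The cost is one sentence and one extra analysis. Sections 7.11 and 12.1a already require central review of TURP tissue, so no new data are needed.

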### 3.9 Data analysis and study power:

As an example of our analytic approach, we present the analysis for the first part of the primary specific aim: the investigation of the association of total dietary fat intake with prostate cancer.

Choice of Statistical Model. We will analyze the association between dietary fat intake and histologically proven presence or absence of prostate cancer using the logistic regression model:

$$\ln \left( \frac{pr(d)}{1-pr(d)} \right) = + \beta_1 x_1 + \beta_2 x_2 + \beta_3 x_3 + \dots$$

The logistic model allows estimation of the effect of the factor of interest ( $x_1$ ), in this case fat intake, on probability of disease ( $pr(d)$ ), while controlling the effects of other factors ( $x_2, x_2, \dots$ ).

We plan to control for age, race, family history and other confounding factors identified during analysis. Parameters in the model will be estimated using maximum likelihood techniques. (38)

We plan two approaches to parametrizing fat intake. First, we will express fat intake as total energy from fat and we will adjust for total energy from other macronutrients (carbohydrate, protein and alcohol). Second, we will express fat intake as percent of energy from fat. We will model the association between fat intake and prostate cancer by categorizing the fat measure into quartiles (using indicator variables in the model), and we will calculate the odds ratios of prostate cancer and their 95% confidence intervals for each quartile of fat intake. We will also conduct a test for trend by representing percent energy from fat as a single variable coded 1 for quartile 1, coded 2 for quartile 2, etc., in the logistic model. This yields an overall estimate of the trend odds ratio for a one quartile increment in fat intake and yields a single significance test for the association of fat intake with prostate cancer. This is the logistic analog to the Mantel-Haenszel test for trend.

We will use similar models to analyze the other variables in the primary specific aim, saturated fat intake and servings of high fat meats and servings of high fat dairy foods, as well as secondary analyses a and b.

Association of Obesity, in Particular Upper Body Obesity with Risk of Prostate Cancer.

We will analyze the association of obesity with prostate cancer using body mass index (BMI) (weight/height) in a logistic model with age, race and height as covariates. We include height as an adjustment factor to account for any remaining confounding of height with body mass index. We will evaluate four models of the association of upper body obesity with prostate cancer, using waist/hip, waist/thigh, abdomen/hip and abdomen/thigh ratios as the primary independent variables, controlling for age, race and body mass index. Including BMI in the model allows separation of any independent effect of upper body obesity from obesity per se. The analysis strategy will be similar to that described for the other exposures of interest; specifically, we will estimate individual odds ratios and confidence intervals for each quartile of obesity or upper body obesity and we will complete an overall test for trend.

Modification of the Effect of Finasteride by Dietary Fat. The final analyses for this study will be conducted to answer whether the effect of finasteride is modified by dietary fat intake. First, we will compute the odds ratios and 95% confidence intervals for the effect of finasteride on prostate cancer separately for the four groups of men categorized by quartiles of percent energy from fat. If these appear to differ (e.g., if finasteride is beneficial for men with the highest level of fat intake but not for those in the lowest level of intake), this is suggestive of modification of the finasteride effect by dietary fat intake.

Second, we will model the interaction between finasteride and dietary fat. To examine this interaction, we will model the relationship between dietary fat, treatment and prostate cancer in a logistic model using the entire study cohort. The model will include the main effect of treatment (finasteride vs. control) and the main effects of dietary fat and an interaction between the two, as well as covariates (age, race, energy intake). If consistent with the data, dietary fat will be modeled as a single trend variable (described under Primary Aim above). This simplifies the interaction, so that a single term would indicate whether the slope of any dietary fat effect on prostate cancer is different for the treatment versus the control group. We will use the interaction term coefficient ( $\beta$ ) and its standard error to determine the magnitude and significance of the modification of the finasteride effect by dietary fat.

Study Power and Minimal Detectable Odds Ratio. Because the sample size of this study is fixed by the PCPT, we present power calculations in terms of the minimal detectable difference in the rate of histologically proven prostate cancer between those in the upper quarter of fat intake (or any nutrient or food group intake),  $p_1$ , and the rate in lower quarter,  $p_0$ .

The difference was computed based on the standard power calculation formula for the difference between groups:

$$= |p_1 - p_0| = \frac{(Z_{0/2} + Z_{\beta})^2 \cdot 2p(1-p)^{1/2}}{n}$$

This formula yields the minimal detectable difference in outcome,  $p_1 - p_0$ , for a study with  $n$  subjects in the upper quartile of food intake and  $n$  subjects in the lower quartile. This difference can then be converted into a minimal detectable odds ratio, which can be interpreted as the minimal odds ratio for the upper quartile of intake versus lower quartile that will yield a 95% CI around the odds ratio that would exclude one.

The assumptions used in the computation were:

1. A two-sided significance level equal to 5%.
2. Power  $(1-\beta)$  equal to 80%.
3. The average outcome,  $p$ , in the combined upper and lower quartile of intake was assumed to be 6%. This is based on the PCPT estimate that 6% of the control group who have biopsies will have detectable prostate cancer at seven years.
4. The number of men in each quartile of intake,  $n$ , was assumed to be 1,350. This was based on 9,000 men to be randomized into the PCPT control arm (proposal), with 60% (5,400) having complete data.

Applying the above assumptions to the equation above yields  $d = .026$ . Translating this difference into  $p_0$  and  $p_1$  and an odds ratio (such that  $(p_0 + p_1)/2 = .06$  and  $p_1 - p_0 = .026$ ) yields  $p_0 = .047$ ,  $p_1 = .073$  and an odds ratio = 1.60. This suggests that the study will have 80% power to detect an odds ratio of prostate cancer of 1.6 for those in the upper versus lower quartile of fat intake or saturated fat intake.

